14.2 Appendix II - Information regarding highly effective contraception methods

Highly effective contraception methods include:

- Total abstinence (when this is in line with the preferred and usual lifestyle of the subject). Periodic abstinence (e.g., calendar, ovulation, symptothermal, post-ovulation methods) and withdrawal are not acceptable methods of contraception
- Female sterilization (have had surgical bilateral oophorectomy with or without hysterectomy), total hysterectomy or tubal ligation at least six weeks before taking study treatment. In case of oophorectomy alone, only when the reproductive status of the woman has been confirmed by follow up hormone level assessment
- Male sterilization (at least 6 months prior to screening). The vasectomized male partner should be the sole partner for that subject.
- Use of oral, injected or implanted hormonal methods of contraception or placement of an intrauterine device (IUD) or intrauterine system (IUS) or other forms of hormonal contraception that have comparable efficacy (failure rate <1%), for example hormone vaginal ring or transdermal hormone contraception (in case of oral contraception you should have been using the same pill on a stable dose for a minimum of 3 months before screening)

14.3 Appendix III - Clinical laboratory tests

Serum chemistry	Hematology	Other
ALT AST Bilirubin - Total and Direct Alkaline phosphatase Serum Creatinine	Complete Blood Count (CBC) Differential (neutrophils, lymphocytes, eosinophils, basophils, monocytes), including reporting of % blasts Platelets Reticulocyte count (absolute and % reticulocytes) optional	Serology: hepatitis A, B, and C HIV Antibody Pregnancy Test: Female patients of childbearing potential only. Serum test at Screening (Section 7). Thiamine blood level (Section 7)
	Coagulation (Required for screening / baseline , optional after enrollment)	
	PT (or INR) PTT	

ALT = alanine aminotransferase, AST = aspartate aminotransferase, PT = prothrombin time, PTT = partial thromboplastin time.

14.4 Appendix IV - Eastern Cooperative Oncology Group performance status

Grade	Performance Status
0	Fully active, able to carry on all pre-disease performance without restriction
1	Restricted in physically strenuous activity but ambulatory and able to carry out work of a light or sedentary nature, e.g., light house work, office work
2	Ambulatory and capable of all self-care but unable to carry out any work activities. Up and about more than 50% of waking hours
3	Capable of only limited self-care, confined to bed or chair more than 50% of waking hours
4	Completely disabled. Cannot carry on any self-care. Totally confined to bed or chair
5	Dead

14.5 Appendix V - Bone marrow biopsy evaluation (when performed, they are not mandatory)

Fibrosis density should be assessed in hematopoietic areas

Fibrosis Grade	Description
0	Scattered linear reticulin with no intersections corresponding to normal bone marrow
1	Loose network of reticulin with many intersections, especially in perivascular areas
2	Diffuse and dense increase in reticulin with extensive intersections, occasionally with only focal bundles of collagen and/or focal osteosclerosis
3	Diffuse and dense increase in reticulin with extensive intersections with coarse bundles of collagen, often associated with significant

Note: Fibrosis density should be assessed in hematopoietic areas. Source: [Tefferi \(2006\)](#).

14.6 Appendix VI - Restricted/prohibited medications

These medications are restricted or prohibited **in combination with INC424**:

Prohibited medications

- Aspirin > 150 mg/day
- Any other investigational medication
- Any other medication for myelofibrosis (these medications must be discontinued prior to Day 1 of INC424 treatment, and all adverse events associated with these medications must be resolved prior to Day 1 of INC424 therapy).
 - Anagrelide
 - Busulfan
 - Hydroxyurea
 - Interferon
 - Lenalidomide
 - Thalidomide

Restricted medications

Use of all CYP3A4 inhibitors is discouraged as they may have effects on plasma levels of INC424; alternative therapies should be considered, if available

Category	Drug Names
Strong inhibitors ^a of CYP3A	boceprevir, clarithromycin, cobicistat, conivaptan, danoprevir/ritonavir, eltegravir/ritonavir, grapefruit juice ¹ , idelalisib, indinavir, itraconazole, ketoconazole, lopinavir/ritonavir, LCL161, mibepradil, nefazodone, neflifavir, posaconazole, ritonavir, saquinavir, sequinavir/ritonavir, telaprevir, telithromycin, voriconazole, indinavir/ritonavir, tipranavir/ritonavir, troleandomycin,
Moderate inhibitors ^b of CYP3A	amprenavir, aprepitant, atazanavir, atazanavir/ritonavir, casopitant, cimetidine, ciprofloxacin, crizotinib, cyclosporin, duranavir, darunavir/ritonavir, diltiazem, dronedarone, erythromycin, faldaprevir, fluconazole ² , fosamprenavir, grapefruit juice ¹ , imatinib, lomitapide, netupitant, nilotinib, schisandra sphenanthera ³ , tofisopam, verapamil
Strong inducers ^c of CYP3A	avasimibe, carbamazepine, enzalutamide, mitotane, phenytoin, rifampin, St. John's wort ³ , rifabutin, phenobarbital,
Moderate inducers ^d of CYP3A	bosentan, efavirenz, etravirine, genistein ³ , lersivirine, lopinavir, modafinil, nafcillin, ritonavir, semagacestat ⁴ , talvirilane ⁴ , thioridazine, tipranavir, ,
The list of CYP inhibitors and inducers was compiled from the FDA's "Guidance for Industry, Drug Interaction Studies;" from the Indiana University School of Medicine's "Clinically Relevant" Table and from the University of Washington's Drug Interaction Database. Note that this may not be an exhaustive list. Please refer to footnotes.	

1. Effect seems to be due to CYP2C19 inhibition by ethinyl estradiol.
2. Fluconazole is a dual CYP3A4 and CYP2C9 inhibitor. Fluconazole is a strong CYP2C9 inhibitor based on the AUC ratio of omeprazole, which is also metabolized by CYP3A; fluconazole is a moderate CYP3A inhibitor.
3. Herbal product.
4. Drugs not available in the US Market.

^aA strong inhibitor for a specific CYP is defined as an inhibitor that increases the AUC of a sensitive substrate for that CYP by equal or more than 5-fold.

^bA moderate inhibitor for a specific CYP is defined as an inhibitor that increases the AUC of a sensitive substrate for that CYP by less than 5-fold but equal to or more than 2-fold

^c A strong inducer for a specific CYP is defined as an inducer that decreases the AUC of a sensitive substrate for that CYP by equal or more than 80%.

^d A moderate inducer for a specific CYP is defined as an inducer that decreases the AUC of a substrate for that CYP by 50-80%.

Dual CYP2C9 and CYP3A4 inhibitors:

Fluconazole avoid the concomitant use of ruxolitinib with fluconazole doses \geq 200 mg daily; If clinically necessary to use doses \geq 200 mg daily consultation with Sponsor is required. Please refer to [Section 6.4.2](#).

14.7 Appendix VII - FACT-Lym Form, Version 4

FACT-Lym (Version 4)

Below is a list of statements that other people with your illness have said are important. Please circle or mark one number per line to indicate your response as it applies to the past 7 days.

PHYSICAL WELL-BEING		Not at all	A little bit	Some-what	Quite a bit	Very much
CP1	I have a lack of energy	0	1	2	3	4
CP2	I have nausea	0	1	2	3	4
CP3	Because of my physical condition, I have trouble meeting the needs of my family	0	1	2	3	4
CP4	I have pain	0	1	2	3	4
CP5	I am bothered by side effects of treatment	0	1	2	3	4
CP6	I feel ill	0	1	2	3	4
CP7	I am forced to spend time in bed	0	1	2	3	4

SOCIAL/FAMILY WELL-BEING		Not at all	A little bit	Some-what	Quite a bit	Very much
CS1	I feel close to my friends	0	1	2	3	4
CS2	I get emotional support from my family	0	1	2	3	4
CS3	I get support from my friends	0	1	2	3	4
CS4	My family has accepted my illness	0	1	2	3	4
CS5	I am satisfied with family communication about my illness	0	1	2	3	4
CS6	I feel close to my partner (or the person who is my main support)	0	1	2	3	4
Q1	Regardless of your current level of sexual activity, please answer the following question. If you prefer not to answer it, please mark this box  and go to the next section.					
CS7	I am satisfied with my sex life	0	1	2	3	4

FACT-Lym (Version 4)

Please circle or mark one number per line to indicate your response as it applies to the past 7 days.

EMOTIONAL WELL-BEING

		Not at all	A little bit	Some- what	Quite a bit	Very much
Q1	I feel sad.....	0	1	2	3	4
Q2	I am satisfied with how I am coping with my illness.....	0	1	2	3	4
Q3	I am losing hope in the fight against my illness.....	0	1	2	3	4
Q4	I feel nervous.....	0	1	2	3	4
Q5	I worry about dying.....	0	1	2	3	4
Q6	I worry that my condition will get worse.....	0	1	2	3	4

FUNCTIONAL WELL-BEING

		Not at all	A little bit	Some- what	Quite a bit	Very much
Q1	I am able to work (include work at home).....	0	1	2	3	4
Q2	My work (include work at home) is fulfilling.....	0	1	2	3	4
Q3	I am able to enjoy life.....	0	1	2	3	4
Q4	I have accepted my illness.....	0	1	2	3	4
Q5	I am sleeping well	0	1	2	3	4
Q6	I am enjoying the things I usually do for fun	0	1	2	3	4
Q7	I am content with the quality of my life right now.....	0	1	2	3	4

FACT-Lym (Version 4)

Please circle or mark one number per line to indicate your response as it applies to the past 7 days.

	ADDITIONAL CONCERNS	Not at all	A little bit	Some-what	Quite a bit	Very much
P2	I have certain parts of my body where I experience pain.....	0	1	2	3	4
L101	I am bothered by lumps or swelling in certain parts of my body (e.g., neck, armpits, or groin).....	0	1	2	3	4
BBM3	I am bothered by fevers (episodes of high body temperature)	0	1	2	3	4
ES3	I have night sweats.....	0	1	2	3	4
LYM0	I am bothered by itching	0	1	2	3	4
LYM2	I have trouble sleeping at night	0	1	2	3	4
BBM6	I get tired easily	0	1	2	3	4
C2	I am losing weight.....	0	1	2	3	4
Q4	I have a loss of appetite.....	0	1	2	3	4
BBM8	I have trouble concentrating.....	0	1	2	3	4
ND	I worry about getting infections	0	1	2	3	4
L106	I worry that I might get new symptoms of my illness.....	0	1	2	3	4
L107	I feel isolated from others because of my illness or treatment.....	0	1	2	3	4
BBM9	I have emotional ups and downs	0	1	2	3	4
L104	Because of my illness, I have difficulty planning for the future	0	1	2	3	4

14.8 Appendix VIII - FACIT Fatigue Scale (Version 4)

FACIT Fatigue Scale (Version 4)

Below is a list of statements that other people with your illness have said are important. Please circle or mark one number per line to indicate your response as it applies to the past 7 days.

		Not at all	A little bit	Some- what	Quite a bit	Very much
1017	I feel fatigued	0	1	2	3	4
1012	I feel weak all over	0	1	2	3	4
An1	I feel listless ("washed out")	0	1	2	3	4
An2	I feel tired	0	1	2	3	4
An3	I have trouble starting things because I am tired	0	1	2	3	4
An4	I have trouble finishing things because I am tired	0	1	2	3	4
An5	I have energy	0	1	2	3	4
An7	I am able to do my usual activities	0	1	2	3	4
An8	I need to sleep during the day	0	1	2	3	4
An12	I am too tired to eat	0	1	2	3	4
An14	I need help doing my usual activities	0	1	2	3	4
An15	I am frustrated by being too tired to do the things I want to do	0	1	2	3	4
An16	I have to limit my social activity because I am tired	0	1	2	3	4

14.9 Appendix IX - MRU concomitant medication

Listed below are the concomitant medications for MPN symptom management that will be recorded for MRU.

GENERIC NAME	INDICATION
ACECLOFENAC	pain
ACETAMINOPHEN	fever, pain
ACETYLSALICYLIC ACID	thrombosis prophylaxis
ACICLOVIR	herpes zoster
ALLOPURINOL	hyperuricemia
AMIKACIN SULFATE	bacterial infection
AMITRIPTYLINE	postherpetic neuralgia
AMOXICILLIN	bacterial infection
AMOXICILLIN W/CLAVULANATE	bacterial infection
AMPHOTERICIN B	fungal infection
ANAGRELIDE	thrombosis prophylaxis
AZTREONAM	bacterial infection
BIOFLAVONOIDS	thrombosis prophylaxis
CARBASALATE CALCIUM	thrombosis prophylaxis
CASPOFUNGIN	fungal infection
CEFEPIME	bacterial infection
CEFOTAXIME SODIUM	bacterial infection
CEFTAZIDIME	bacterial infection
CEFTRIAXONE	bacterial infection
CEFUXOME	bacterial infection
CELECOXIB	pain
CETIRIZINE	pruritus
CIPROFLOXACIN	bacterial infection
CLARITHROMYCIN	bacterial infection
CLAVULANIC ACID	bacterial infection
CLINDAMYCIN	bacterial infection
CLOPIDOGREL	thrombosis prophylaxis
CLOTRIMAZOLE	fungal infection
CODEINE PHOSPHATE	pain
CO-TRIMOXAZOLE	bacterial infection
DALTEPARIN	thrombosis prophylaxis
DANOCRINE (Danazol®)	myelofibrosis
DARBEPoETIN ALFA	anemia
DEFERASIROX	iron overload
DEFEROXAMINE MESILATE	iron overload
DEXIBUPROFEN	pain
DICLOFENAC	pain
DIHYDROCODEINE	pain
DIMENHYDRINATE	nausea
DIMETINDENE	pruritus

GENERIC NAME	INDICATION
DIPHENHYDRAMINE	pruritus
DIPYRIDAMOLE	thrombosis prophylaxis
DOXYCYCLINE	bacterial infection
ENOXAPARIN	thrombosis prophylaxis
EPOETIN ALFA	anemia
EPOETIN BETA	anemia
ERYTHROMYCIN	bacterial infection
ESOMEPRAZOLE	gastritis-reflux
ETOENAMATE	pain
ETORICOXIB	pain
FENTANYL	pain
FILGRASTIM	leukopenia
FLUCLOXACILLIN	bacterial infection
FLUCONAZOLE	fungal infection
FUROSEMIDE	edema
FUSIDIC ACID	bacterial infection
GABAPENTIN	postherpetic neuralgia
GENTAMICIN	bacterial infection
HEPARIN	thrombosis prophylaxis
HYDROCHLOROTHIAZIDE	edema
HYDROMORPHONE HYDROCHLORIDE	pain
IBUPROFEN	pain
IMIPENEM	bacterial infection
INDOBUFEN	thrombosis prophylaxis
KETOPROFEN	pain
LEVOFLOXACIN	bacterial infection
LIDOCAINE HYDROCHLORIDE	pain
LINEZOLID	bacterial infection
LORATADINE	pruritus
MEFENAMIC ACID	pain
MEROPENEM	bacterial infection
METAMIZOLE	fever, pain
METOCLOPRAMIDE HYDROCHLORIDE	nausea
MINOCYCLINE HYDROCHLORIDE	bacterial infection
MORPHINE	pain
MOXIFLOXACIN	bacterial infection
NADROPARIN	thrombosis prophylaxis
NAPROXEN	pain
NIMESULIDE	fever, pain
NITROFURANTOIN	bacterial infection
NORFLOXACIN	bacterial infection
OFLOXACIN	bacterial infection
OMEPRAZOLE	gastritis-reflux
ONDANSETRON	nausea

GENERIC NAME	INDICATION
OXYCODONE	pain
PALONOSETRON HYDROCHLORIDE	nausea
PANTOPRAZOLE	gastritis-reflux
PARACETAMOL	fever, pain
PARACETAMOL W/TRAMADOL	pain
PETHIDINE HYDROCHLORIDE	pain
PHENPROCOUMON	thrombosis prophylaxis
PIPERACILLIN	bacterial infection
PIPERACILLIN/TAZOBACTAM	bacterial infection
PIROXICAM	pain
PLATELETS, CONCENTRATED	thrombocytopenia
PREDNISOLONE	fever prophylaxis
PRIMAXIN	bacterial infection
PRISTINAMYCIN	bacterial infection
PROPRANOLOL	prophylaxis of variceal bleeding
RANITIDINE	gastritis-reflux
RED BLOOD CELLS, CONCENTRATED	anemia
ROXITHROMYCIN	bacterial infection
SPIRONOLACTONE	edema
TICLOPIDINE	thrombosis prophylaxis
TOBRAMYCIN SULFATE	bacterial infection
TORASEMIDE	edema
TRAMADOL	pain
TRIMETHOPRIM	bacterial infection
VALACYCLOVIR	herpes zoster
VALORON N	pain
VANCOMYCIN HYDROCHLORIDE	bacterial infection
VORICONAZOLE	fungal infection
WARFARIN	thrombosis prophylaxis
XIPAMIDE	edema

1.1 Study design

This is a phase IIIB, multicenter, single-arm, open-label expanded access study intended to provide additional data on the safety and efficacy of INC424 in patients with PMF or PPV MF, or PET-MF who have either received prior treatment or who have never received treatment.

Patients will be screened within four weeks prior to the first dose of INC424.

Baseline evaluations will be performed within a week of the first dose of INC424.

Visits will occur on a monthly basis for the first 3 months, then every 3 months thereafter and at study discontinuation.

In this document, study drug refers to INC424.

For this study, study drug will be administered continuously. All patients will be treated with oral INC424 at a dose of 5 - 25 mg (dose based on baseline platelet count) BID until one of the following occurs: disease progression; transplant; unacceptable toxicity; death; discontinuation from the study for any other reason; withdrawal of consent; physician decision; until the study drug becomes commercially available in each participating country or until 24- months after last patient first visit (LPFV), or the project is discontinued, whichever occurs first.

If it is determined at any study visit that the patient will discontinue study drug that day, then that study visit will be the end-of-study visit, and the end-of-study visit procedures will be followed. (Refer to protocol section 7.6.2)

An interim analysis planned for this study will take place when 50 patients with low platelets will have completed 6 months of treatment. Additional analyses may also be performed if needed to fulfill regulatory obligation or publication purpose.

The final analysis will be performed after all patients have either completed the study or have been prematurely discontinued from the study.

1.2 Study objectives and endpoints

This study is intended to collect additional safety of INC424 in patients with PMF or PPV MF, or PET-MF.

1.2.1 Primary Objective

- To collect additional safety of INC424 in patients with PMF, PPV MF, or PET-MF, who have either received prior treatment with commercially available agents or who have never received treatment.

1.2.2 Secondary Objectives:

- To document the best overall response rate to INC424 in patients with PMF, PPV MF, or PET-MF as evaluated by the Investigator.
- To collect quality of life (QoL) endpoints in patients with PMF, PPV MF, or PET-MF treated with INC424.
- To document medical resource utilization (MRU) in patients with PMF, PPV MF, or PET-MF treated with INC424.

2 Patients and Treatments:

Eligible patients for this Expanded Access study are male or female aged ≥ 18 years who are diagnosed with PMF or PPV MF or PET-MF and who have either never received treatment, or who have received prior treatment with commercially available agents or have previously received INC424, patients with high risk OR intermediate risk level 2 OR intermediate risk level 1 with an enlarged spleen.

Patients who are **not** eligible for this Expanded Access study are patients with active hepatitis A, B, C or who are HIV-positive, and patients with coagulation parameters (PT, PTT, or INR) $\geq 1.5 \times$ ULN.

2.1 Analysis sets

Full Analysis Set (FAS) consists of all patients who received at least one administration of study drug.

Safety Set (SS) consists of all patients who received at least one dose of study drug and had at least one post-baseline safety assessment.

Please note: the statement that a patient had no adverse events (on the Adverse Event CRF) constitutes a safety assessment. Patients who have received at least one dose of study drug but who have no post-treatment safety data of any kind would be excluded from the safety population.

Per protocol set (PPS) consists of all FAS patients without any major protocol deviation.

The following major protocol deviations will lead to exclusion from the PPS:

- Male or female patients aged < 18 years of age at screening (Deviation code: I03)
- Unconfirmed diagnosis of PMF, PPV-MF or PETMF at screening (Deviation code: I04).
- Secondary MF (PPV-MF or PETMF) grade 0 and 1 for Fibrosis on scale 0-3. or grade 0, 1 and 2 on scale 0-4 at screening (Deviation code: I13).

The Full analysis set will be used for all population and efficacy analyses, while Safety set will be used for treatment administration description and safety analyses.

2.2 Subgroup definitions

No sub-group analyses are planned for this study.

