6.1 Investigational treatment, other study treatment, supportive treatment

6.1.1 Study drug dosing

All eligible patients with PMF, PPV MF, or PET MF who consent to participate in this study will receive INC424 open-label investigational drug provided free of charge by Novartis Pharmaceuticals at a dose of 5 – 25 mg BID [dose based on Baseline platelet count] until either:

[figure not shown]
- Disease progression;
- Transplant;
- Unacceptable toxicity;
- Death;
- Discontinuation from the study for any other reason;
- Physician decision
- Withdrawal of informed consent;
- Until 24-months after LPFV; or
- Until the drug is commercially available, whichever occurs first.

The starting dose of INC424 will be determined based on baseline platelet counts as follows:

- Patients with a baseline platelet count of > 200,000/ μ L will begin dosing at 20 mg PO BID.
- Patients with a baseline platelet count of between 100,000/ μ L – 200,000/ μ L (inclusive) will begin dosing at 15 mg PO BID.
- Patients with a Baseline platelet count of 50,000/ μ L – <100,000/ μ L / μ L will begin dosing at 5 mg BID (one 5 mg tablet BID)
- Patients with platelet counts less than 50,000/ μ L are ineligible for the study (see [Section 5.2](#) and [Section 5.3](#)).

Dosage Tablet Combinations for Patients

For 25 mg PO BID	For 20 mg PO BID	For 15 mg PO BID	For 10 mg PO BID	For 5 mg PO BID
Two 10 mg tablets	Four 5 mg tablets	One 10 mg tablet and	One 10 mg tablet	One 5 mg tablet

For 25 mg PO BID	For 20 mg PO BID	For 15 mg PO BID	For 10 mg PO BID	For 5 mg PO BID
and one 5mg tablet		one 5 mg tablet		
One 10 mg tablet and three 5 mg tablets	Two 10 mg tablets	Three 5mg tablets	Two 5 mg tablets	
Five 5 mg tablets	Two 5 mg tablets and one 10 mg tablet			

INC424 tablets will be administered orally without regards to food in an outpatient setting in accordance with the specified dosing schedules. The dosage strength is 5 mg or 10 mg per tablet INC424. INC424 tablets are to be taken orally BID, approximately 12 hours apart (morning and night). INC424 will be self-administered by the patient, and each investigator should instruct the patient to take the study drug as per protocol (if applicable). All dosages prescribed and dispensed to the patient and all dose changes during the study must be recorded on the Dosage Administration Record (DAR) eCRF.

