The primary analysis will be performed after all patients have either completed 24 months of treatment or have been prematurely discontinued from the study. All patients should have been followed for 28 days after they have discontinued INC424, data collected during this follow-up period will be included in the analysis. An interim analysis planned for this study will take place when 50 patients with low platelets will have completed 6 months of treatment.

Additional analyses may also be performed if needed to fulfill regulatory obligation or publication purpose.

Statistical reporting and grouping

Data will be analyzed according to platelet count at baseline and displayed considering the following two groups:

- Low platelet patients (platelets < 100, 000 / μ L)
- and non-low platelets (platelets \geq 100, 000 / μ L).

[figure not shown]
All analyses for categorical data will be presented as frequencies and percentages (% based on number of patients from the considered population unless specified otherwise).

For all continuous data, except time related ones, the following descriptive statistics will be presented: n, mean, standard deviation, median, minimum and maximum. Time related data (i.e. durations such as overall survival) will be summarized using n, median, minimum and maximum.

For all analyses, **baseline value** will be defined as the latest available assessment obtained prior to the date of first dose of study drug administration. If assessment prior to first dose of study drug administration is not available, then assessment on the day of first dose of study drug administration will be used at baseline.

All data considered in the analysis will be listed individually.

Please note: due to the trial design and intent, it is not possible to ensure that a sufficient number of patients will be available to conduct the analyses as planned. Therefore, it is important to consider that certain analyses described in the subsequent section may not be relevant if study population is too small.

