11.5.1 Variables

Primary analysis will be performed on the **incidence of treatment-emergent AEs**.

Incidence of a given AE is defined as the ratio of total number of patients experiencing at least once this AE (defined by its preferred term) divided by the total number of patients in the safety set.

A treatment-emergent AE is an AE that starts during treatment (including the 28 days following last treatment administration) or worsen on treatment.

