3.4.1 Primary endpoints

3.4.1.1 Variables

The analysis of the primary endpoint will be performed on the incidence by patients of **treatment-emergent AEs** considering or not certain AEs characteristics (e.g. relationship to study medication, severity).

Incidence of a given AE is defined as the ratio of total number of patients experiencing the given AE at least once (defined by its preferred term [PT]) divided by the total number of patients at risk (i.e. part of the safety set).

A treatment-emergent AE is an AE that first occurs or worsens during treatment (including the 28 days following last treatment administration).

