3.7 Interim analyses

An interim analysis will be performed to closely monitor safety, and ensure an appropriate risk/benefit ratio in the patient population with low platelet counts, between 50,000 and 100,000/ μ L. In order to adequately assess the risk/benefit ratio, this analysis will also be performed on non-low platelet patients ($\geq 100,000/\mu$ L), which will be further detailed in analysis plan, who will serve as an internal reference population. This interim analysis will take place when 50 patients with low platelets have completed 6 months of treatment.

Analyses may be performed if needed to fulfill regulatory obligations, to comply with post-approval commitments or for publication purposes.

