3.11.3 Dynamic International Prognostic Scoring System (DIPSS)

The DIPSS can be used to assess a patient's prognosis as conditions change over time.

The risk level is assigned by the total score:

4 Change to protocol specified analyses

The definitions for the transfusion dependence at baseline, new onset of transfusion dependence and new transfusion independency (protocol v05 section 11.6.4.1) are not current. For the final analysis these definition have been updated as per IWG MRT 2013 ([section 3.6](#) of this SAP).

Clinical Study Report

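### Protocol section 11 calls for results by baseline platelet group; the SAP specifies no such display for the final analysis and does not declare the change

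*SAP*

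**What the plan says.** Protocol section 11, under *Statistical reporting and grouping*, states: "Data will be analyzed according to platelet count at baseline and displayed considering the following two groups". The groups are below 100,000/µL, and 100,000/µL or above. A closing note in the same section allows that some analyses "may not be relevant if study population is too small".

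Protocol 6.1.1 sets the starting dose by baseline platelet count. Patients from 50,000 to below 100,000/µL "will begin dosing at 5 mg BID (one 5 mg tablet BID"; those at 100,000/µL or above start at 15 or 20 mg BID.

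SAP 2.2 reads in full: "No sub-group analyses are planned for this study". SAP 3.7 keeps a platelet comparison at the interim analysis, triggered when 50 low-platelet patients have 6 months of treatment, and adds that "this analysis will also be performed on non-low platelet patients". SAP 4, the place for departures from the protocol, lists one item: "The definitions for the transfusion dependence at baseline, new onset of transfusion dependence and new transfusion independency (protocol v05 section 11.6.4.1) are not current".

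**The concern.** The SAP appears to withdraw a protocol commitment on the primary (safety) objective without saying so. A statistician working from the SAP alone would build final adverse event tables with a single column.

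The low-platelet patients are those about whom least was known. The protocol synopsis describes safety data in thrombocytopenic myelofibrosis as limited, and the two low-platelet studies summarised in protocol 1.3.4 report 20 and 41 patients. The cut at 100,000/µL also largely follows the starting-dose tiers, so a pooled table mixes patients started on quite different doses. The interim look does not replace the final display: patients and follow-up accrued after its cut-off enter only the final analysis.

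**Working it through.** **Text comparison**

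1. *Scope of the protocol rule.* It stands in the section 11 preamble beside the rules on summary statistics and the definition of baseline, which apply to all analyses. The interim analysis has its own section (11.7). Nothing ties the grouping to the interim.
2. *Platelets in the SAP's final-analysis sections.* They appear as a baseline characteristic (3.1.2), a change-from-baseline parameter (3.4.3), part of hematology (3.5.2) and a transfused component (3.6). They are never a grouping variable.
3. *Adverse event tables.* SAP 3.4.1 and 3.5.1 tabulate by system organ class, preferred term, grade, relationship, seriousness and action taken, with no platelet split.
4. *Declared changes.* SAP 4 covers the transfusion definitions only.
5. *Overall incidence.* Protocol 11.5.1 uses patients with the event "divided by the total number of patients in the safety set"; SAP 3.4.1.1 uses patients with the event "divided by the total number of patients at risk (i.e. part of the safety set". These agree.

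**Arithmetic, for illustration only**

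The plan has no figure to reproduce: the study is descriptive, and the maximum of 2500 comes from country assessments.

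*Precision of a low-platelet column.* The 95% half-width at 50% incidence is 1.96 × √(0.25/n). Accrual was approaching 950 when platelet counts below 100,000/µL became eligible (Amendment 2), so at most about 2238 − 950 = 1288 patients entered afterwards. Two population shares are available: 16.5% below 100,000/µL at diagnosis (synopsis), and 25% to 30% (Amendment 2 rationale).

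| Assumed n | Basis | Half-width (points) |
|---|---|---|
| 50 | interim trigger | 13.9 |
| 213 | 16.5% of 1288 | 6.7 |
| 322 | 25% of 1288 | 5.5 |
| 386 | 30% of 1288 | 5.0 |
| 2238 | all enrolled | 2.1 |

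None of the low-platelet sizes is an estimate. Counts of 50,000 to 75,000/µL were admitted only from Amendment 3, the 16.5% includes counts below 50,000/µL that were never eligible, and the synopsis expects a higher share in intermediate and high-risk disease.

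*What pooling could hide.* Pooled rate = w × p(low) + (1 − w) × p(non-low), where w is the low-platelet share. Take p(non-low) = 12.9%, the grade 3/4 thrombocytopenia rate quoted for COMFORT-I, and assume p(low) is double, 25.8%:

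- w = 50/2238 = 2.2%: pooled 13.2%
- w = 16.5%: 0.165 × 25.8 + 0.835 × 12.9 = 15.0%
- w = 30%: 0.30 × 25.8 + 0.70 × 12.9 = 16.8%

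If the two rates were equal, the pooled rate would be 12.9% and nothing would be hidden. The documents do not say which case applies.

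**The case against.** The strongest reply is that a display grouping is not a sub-group analysis, so SAP 2.2 may not have been meant to remove it, and columns are usually fixed in table shells, which are not available here. This has force. A reader might infer that low-platelet incidence will definitely not be reported; the documents do not go that far. But no SAP section specifies the display either, and if the shells do split the tables, SAP 2.2 should say so.

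The protocol's support is also thin. The grouping appears once, the synopsis statistics entry omits it, and sections 11.5 to 11.5.2 do not repeat it. It is still current protocol text, stated as a general rule. The caveat about small numbers could excuse a sparse table, but the SAP does not invoke it. SAP 3.7 does preserve the platelet comparison that has a stated risk/benefit purpose, though only at the interim.

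Three other stronger readings are tempting:

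- *That the phase I/II trial supports a cut at 100,000/µL, or sizes the difference.* Protocol 1.3.4.1 does report more thrombocytopenia at lower baseline counts, but lower there means below 200 × 10⁹/L, and the synopsis says no patient in that trial started below 100,000/µL. The contrast lies wholly inside this study's non-low group.
- *That platelet group and starting dose are the same thing.* Protocol 6.2.2.3 and 6.2.2.4 also reduce starting doses for severe renal and any hepatic impairment, so the match is close but not exact.
- *That the primary incidence is defined differently in the two documents.* It is not.

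**Conclusion.** The discrepancy is real and undeclared: the protocol calls for results by two baseline platelet groups, and the SAP specifies none for the final analysis. It should be fixed before the final tables are run. It does not invalidate the overall safety results.

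Confidence is high on the text comparison. It is lower on the consequence, because that rests on the SAP text alone. The amount of masking is unknown. A low-platelet column would have a half-width of roughly 5 to 14 points at 50% incidence under the assumed group sizes, against about 2 for the total; that describes the precision of the remedy, not the harm.

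**What to change.** Replace SAP 2.2 with: *Final analyses are displayed by baseline platelet count (<100,000/µL; ≥100,000/µL) and in total, as specified in protocol section 11; patients with no baseline platelet count appear in the total only.* Because the protocol rule covers data generally, this should extend to patient-reported outcomes, resource use, vital signs and concomitant medication as well as adverse events.

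Add a note to the adverse event tables: *Platelet thresholds for mandated dose changes differ by starting dose (protocol Tables 6-2 and 6-3), so thrombocytopenia rates are not directly comparable across columns.* The reason is that a laboratory value requiring a change in study drug counts as an adverse event (protocol 9.1.1). At 80,000/µL, for example, Table 6-2 mandates a reduction for a patient on 15 mg BID, while Table 6-3 requires none for a 5 mg BID starter. Separately, the general hold below 50,000/µL in protocol 6.2.2 and the reduction band in Table 6-3 do not agree and must be reconciled; the note does not depend on how.

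If the sponsor prefers to drop the grouping for some or all tables, declare and justify that in SAP 4.

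The cost is SAP wording, one table note and extra columns. No new data are needed, because the baseline platelet count already sets the starting dose. The downside is longer tables and a less precise low-platelet estimate.
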